### Secondary Efficacy Analysis

Continuous efficacy variables will be summarized using descriptive statistics for the observed data and change and/or percent change from baseline by treatment group and visit as appropriate.

Change from baseline to Week 52 in NAS and individual histological scores will be analyzed in an analysis of covariance model, adjusting for treatment (300 mg NST-4016, 600 mg NST-4016, or placebo), biopsy fibrosis score (2 levels: F1 versus F2 or F3), and respective baseline score. Pairwise treatment comparisons between each NST-4016 dose and placebo will be estimated in this model using least square (LS) means, standard errors, 95% confidence intervals, and p-values. A similar analysis will be carried out for the imaging parameters at Week 16 and Week 52.

Efficacy variables measured at multiple timepoints will be analyzed with Mixed Model Repeated Measures methods, with change (or percent change) from baseline as the dependent variable, adjusting for treatment (300 mg NST-4016, 600 mg NST-4016, or placebo), biopsy fibrosis score (2 levels: F1 versus F2 or F3), and baseline score. Pairwise treatment comparisons between each NST-4016 dose and placebo at Week 52 will be estimated using LS means, standard errors, 95% confidence intervals, and p-values.

### **Exploratory Biomarker Analysis**

The analysis of exploratory endpoints will be further described in the Statistical Analysis Plan.

### **Pharmacokinetic Analysis**

Trough plasma PK concentrations at Visits 3 to 9 will be summarized descriptively by visit for the Trough PK Population.

For the subset of patients with intensive PK sampling data, additional PK parameters will be summarized by treatment using descriptive statistics for the Intensive PK Population. No formal statistical analysis of PK parameters will be performed.

### **Safety Analysis**

Safety variables will be tabulated and presented for the Safety Population.

Baseline will be defined as the predose value at Visit 2 (Week 0); if this value is missing, then the latest predose value will be used.

A TEAE is defined as a new or worsening adverse event after the first dose of study drug. The number and percentage of patients with at least 1 TEAE will be summarized by treatment group by system organ class and preferred term. Similar summaries will be presented for study drug-related TEAEs and SAEs.

Safety laboratory parameters, vital signs, and ECGs will be summarized by treatment group by visit. Change from baseline values by visit will also be presented for the continuous parameters. The number (and percentage) of patients with abnormalities based on predefined normal ranges will be tabulated by treatment group.

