### **SAMPLE SIZE DETERMINATION:**

A sample size of 88 patients per treatment group provides 80% power to detect a 40% responder rate for active versus placebo, assuming a placebo response rate of 18% and a dropout rate of 25%.

**SITES:** Approximately 50 sites in the United States

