## Source: Study NST-02 interim analysis (data on file) 1.4.1.3 Clinical safety

A safety review was performed of the 157 patients screened at the time of the Week 16 interim analysis with the treatment-emergent adverse events (TEAEs) presented in Table 2. There was no notable difference in the frequency, severity, or causality of the overall safety profile between placebo and either 300 mg or 600 mg of icosabutate for up to 16 weeks. The majority of TEAEs were mild to moderate in severity and generally comparable across the study arms. The treatment was well tolerated and comparable to placebo, with the exception of mild nausea (4.3%, 9.0%, and 21.3% in placebo, 300 mg, and 600 mg, respectively).

Table 2. Overview of TEAEs by Treatment Arm in Study NST-02

	Placebo (n=46)	Icosabutate 300 mg (n=46)	Icosabutate 600 mg (n=47)	
Any TEAE (n [%])	37 (80.4%)	30 (65.2%)	37 (78.75%)	
Maximum severity				
Grade 1 (n [%])	12 (26.1%)	7 (15.2%)	9 (19.1%)	
Grade 2 (n [%])	24 (52.2%)	22 (47.8%)	20 (42.6%)	
Grade 3 (n [%])	1 (2.2%)	1 (2.2%)	4 (8.5%)	
Grade 4 (n [%])	0 (0.0%)	0 (0.0%)	0 (0.0%)	
Grade 5 (n [%])	0 (0.0%)	0 (0.0%)	0 (0.0%)	
Drug-related TEAE (n [%])	7 (15.2%)	7 (15.2%)	8 (17.0%)	
SAE (n [%])	1 (2.2%)	1 (2.2%)	3 (6.4%)	
Drug-related SAE (n [%])	0 (0.0%)	0 (0.0%)	0 (0.0%)	
SAE = serious adverse event; TEAE = treatment-emergent adverse event. Source: Study NST-02 interim analysis (data on file)				

No confirmed drug-induced liver injury, cardiovascular events, or worsening of diabetes were observed during the study period. Laboratory values remained stable or improved and there were no clinically relevant changes in vital signs or electrocardiograms (ECGs). No safety or tolerability signals of concern were observed during the study period as confirmed by an independent unblinded DSMC review. In summary, the safety and tolerability of icosabutate remains favorable and similar to that observed in other patient populations.

ALP = alkaline phosphatase; ALT = alanine aminotransferase; ApoC3 = apolipoprotein C3; AST = aspartate aminotransferase; ELF = enhanced liver fibrosis; GGT = gamma glutamyl transferase; HbA1c = hemoglobin A1c; HDL-C = high-density lipoprotein-cholesterol; HOMA-IR = Homeostatic Model Assessment of Insulin Resistance; hsCRP = high-sensitivity C-reactive protein; LDL-C = low-density lipoprotein-cholesterol; Pro-C3 = N-terminal type 3 collagen propeptide; TG = triglyceride.

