# 6.5 Early Termination Visit and Withdrawal Procedures

The end of treatment for patients completing the study is Visit 9 (Week 52). For patients who are withdrawn from the study prior to completion, all Visit 9 procedures will be performed at an ET Visit. Liver biopsy at ET will only be performed for patients who have been on study drug for at least 6 months.

Patients who discontinue early from the study for any reason prior to completion of the treatment period will be requested to return to the clinic for an ET Visit as soon as possible after their last intake of study drug.

If a patient discontinues early from the study for any reason after completion of the treatment period but before the Safety Follow-up Visit, sites should make every attempt to bring the patient into the site for the Safety Follow-up Visit.

The following procedures will be performed at the ET Visit:

- Record concomitant medications.
- Measure body weight.
- Perform complete physical examination.
- Collect vital signs (blood pressure [3 readings], pulse rate, and body temperature) with the patient in the sitting position after 5 minutes of rest and before any blood draws.
- Collect fasting blood sample for the following:
  - o Hematology, biochemistry, coagulation, and lipid panels.
  - Lipoprotein particle size.
  - o Biomarkers (HOMA-IR, hsCRP, Pro-C3, and ELF panel).
  - o Serum pregnancy test (only for women of childbearing potential).
  - o Lipidomic analyses (in a subgroup of patients).
- Collect urine sample for urinalysis.
- Perform 12-lead ECG after the patient has been resting in the supine position for at least 10 minutes.
- Perform MRI-PDFF and cT1 imaging.
- Perform liver biopsy (if patient has been on study drug for at least 6 months) for analyses (including lipidomics in a subset of patients).
- Assess adverse events.
- Collect a PK blood sample.
- Collect returned and used/unused study drug and assess compliance.

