#### 8 SAFETY ASSESSMENTS

#### **8.1** Adverse Events

An adverse event is defined as any untoward medical occurrence in a clinical investigation patient administered a pharmaceutical product, which does not necessarily have a causal relationship with this treatment. An adverse event can therefore be any unfavorable and/or unintended sign (including an abnormal laboratory finding), symptom, or disease temporally associated with the use of an investigational medicinal product, whether or not related to the investigational medicinal product. All adverse events, including observed or volunteered problems, complaints, or symptoms, are to be recorded on the appropriate eCRF.

Adverse events, which include clinical laboratory test variables, will be monitored and documented from the time the patient signs the informed consent form (ICF) until Visit 10 (Week 54) or the ET Visit (if applicable). Patients should be instructed to report any adverse event that they experience to the Investigator, whether or not they think the event is due to study treatment. Investigators should make an assessment for adverse events at each visit and record the event on the appropriate adverse event eCRF.

Wherever possible, a specific disease or syndrome rather than individual associated signs and symptoms should be identified by the Investigator and recorded on the eCRF. However, if an observed or reported sign or symptom is not considered a component of a specific disease or syndrome by the Investigator, it should be recorded as a separate adverse event on the eCRF. Additionally, the condition that led to a medical or surgical procedure (eg, surgery, endoscopy, tooth extraction, or transfusion) should be recorded as an adverse event, not the procedure itself.

Any medical condition already present at screening should be recorded as medical history and not be reported as an adverse event unless the medical condition or signs or symptoms present at screening changes in severity, frequency, or seriousness at any time during the study. In this case, it should be reported as an adverse event.

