# 8.3 Serious Adverse Event Reporting – Procedures for Investigators

## **Initial reports**

All SAEs occurring from the time of informed consent until 30 days following the last dose of study drug must be reported to Medpace Clinical Safety within 24 hours of the knowledge of the occurrence. After the 30-day reporting window, any SAE that the Investigator considers related to study drug must be reported to the Medpace Clinical Safety or Sponsor designee.

To report the SAE, complete the SAE form electronically in the Electronic Data Capture (EDC) system for the study. When the form is completed, Medpace Safety personnel will be notified electronically by the EDC system and will retrieve the form. If the event meets serious criteria and it is not possible to access the EDC system, send an email to Medpace Safety at [contact] or call the Medpace SAE reporting line (phone number listed below), and fax/email the completed paper SAE form to Medpace (contact information listed in Section 8.6) within 24 hours of awareness. When the EDC system becomes available, the SAE information must be entered within 24 hours of the system becoming available.

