3.6.1 Adverse Events (AEs)

An adverse event is defined as any untoward medical occurrence in a clinical investigation patient administered a pharmaceutical product, which does not necessarily have a causal relationship with this treatment. An adverse event can therefore be any unfavorable and/or unintended sign (including an abnormal laboratory finding), symptom, or disease temporally associated with the use of an investigational medicinal product, whether or not related to the investigational medicinal product. A treatment emergent AE (TEAE) is defined as a new or worsening adverse event after the first dose of study drug.

All AEs will be coded to system organ class and preferred term using MedDRA version 22.0.

An overview of AEs will be provided including counts and percentages of patients and number of events by treatment group and overall for Safety Population (and event counts) with the following:

- Any Adverse Event
- Any TEAEs
- Maximum severity of TEAEs
- Study drug related TEAEs
- Maximum severity of study drug related TEAEs
- TEAEs leading to discontinuation of study drug
- Any TEAEs of special interest (TEAESI)
- Any serious TEAEs (TESAEs)
- Study drug related TESAEs
- TESAE/TEAESIs leading to discontinuation of study

- TESAEs leading to death
- TESAEs related to COVID leading to death

The TEAEs described above will be summarized separately by System Organ Class and Preferred Term (and by maximum severity).

Listings will be presented specifically for all TEAEs, TEAESI, TESAEs, TEAEs Leading to Discontinuation of Study Drug, TEAEs Leading to Discontinuation of Study and TESAEs Leading to Death.

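### Adverse events are summarised as percentages of all dosed patients and raw event counts, with no allowance for time at risk; if dropout differs by arm, later-onset risk is understated in the arm that loses more patients

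*Protocol*

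**What the plan says.** Protocol 9.2.2 and the synopsis plan that "The number and percentage of patients with at least 1 TEAE will be summarized by treatment group by system organ class and preferred term", with similar summaries for drug-related TEAEs and SAEs. SAP 3.6.1 plans "counts and percentages of patients and number of events by treatment group and overall for Safety Population" and lists subsets such as maximum severity and TEAEs leading to discontinuation of study drug. The denominator is the Safety Population, meaning everyone who took at least one dose. Neither document plans a person-time rate, a time-to-first-event or cumulative-incidence summary, or an interval around any AE contrast.

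The length of observation differs by patient:

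- Protocol 8.1 collects AEs "until Visit 10 (Week 54) or the ET Visit (if applicable".
- Protocol 6.5 asks early leavers to "return to the clinic for an ET Visit as soon as possible after their last intake of study drug", whereas completers are seen 14 days after the last dose.
- SAEs have a longer window (Protocol 8.3): "All SAEs occurring from the time of informed consent until 30 days following the last dose of study drug must be reported". Related SAEs are also reported after that.

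The sample size is set "assuming a placebo response rate of 18% and a dropout rate of 25" per cent, a single figure with no split by arm. SAP 3.3.7 derives weeks of exposure and tabulates them by arm. SAP 3.3.1 tabulates early withdrawal and its primary reason by arm. Neither is linked to the AE tables.

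**The concern.** A patient who leaves at week 6 counts as a whole patient in the denominator but could contribute non-serious AEs for only about six weeks. If one arm has more such patients, its percentage falls for reasons unrelated to the drug.

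Safety and tolerability is the protocol's only secondary objective, and the plan expects to lose about a quarter of its patients. The interim review reports "mild nausea (4.3%, 9.0%, and 21.3% in placebo, 300 mg, and 600 mg, respectively". That does not show unequal retention, but it is a reason not to build the safety analysis on the assumption that retention is equal. What is at stake is the dose-versus-placebo comparison for events that begin, or keep occurring, after the first weeks of a 52-week treatment period.

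**Working it through.** **The plan's own figure.** The 25% enters only through the sample size. For 18% v 40%, two-sided alpha 0.05 and 80% power, with pooled variance under the null:

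n = [1.96 √(2 × 0.29 × 0.71) + 0.8416 √(0.18 × 0.82 + 0.40 × 0.60)]² / 0.22² = 65.6, so 66 per arm.

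66 / 0.75 = 88, which is the stated number. The plan therefore does budget for this loss.

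**Inputs for the AE check.** The documents give 52 weeks of treatment and 25% dropout overall. The rest is assumed: a one-year AE risk of 30% in both arms, dropout independent of AEs, and the dropout splits and timing below.

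**Formula.** With dropout proportion d and leavers going uniformly over weeks 0 to W:

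crude risk = d × m + (1 − d) × 0.30

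Here m is a leaver's average chance of an event before leaving. For a constant hazard, λ = −ln(0.70)/52 = 0.00686 per week and m = 1 − (1 − e^(−λW))/(λW).

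- W = 26: m = 0.084.
- W = 52: m = 0.159.
- Hazard confined to the first 8 weeks, W = 26: m = (8/26) × 0.159 + (18/26) × 0.30 = 0.257.

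Example, 30% v 20% dropout, W = 26: (0.30 × 0.084 + 0.70 × 0.30) / (0.20 × 0.084 + 0.80 × 0.30) = 0.235 / 0.257 = 0.92.

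**Crude risk ratio when the true ratio is 1.00** (arm with more dropout v the other arm):

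| Dropout | Leavers over 52 weeks | Leavers in first 26 weeks | First 26 weeks, hazard in first 8 weeks |
|---|---|---|---|
| 25% v 25% | 1.00 | 1.00 | 1.00 |
| 30% v 20% | 0.95 | 0.92 | 0.985 |
| 35% v 15% | 0.90 | 0.84 | 0.970 |
| 40% v 10% | 0.85 | 0.77 | 0.956 |

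With a true hazard ratio of 1.5 and full follow-up, the risk ratio is (1 − 0.70^1.5)/0.30 = 0.414/0.30 = 1.38. Under constant hazard, the three unequal splits give crude ratios of 1.32, 1.25 and 1.19 (leavers over 52 weeks) or 1.27, 1.17 and 1.07 (first 26 weeks).

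**Cross-check.** With exponential dropout over the year and a true risk of 20%, the null ratios are 0.94, 0.88 and 0.83, close to the 52-week column. In that model 25% dropout cuts mean follow-up from 52 to 45.2 weeks, and a true 20% appears as 17.5% in every arm.

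**Would a patient-year rate solve it?** Under constant hazard, yes: the rate ratio returns to 1.00. With the hazard confined to the first 8 weeks it overcorrects, because the arm with more leavers loses late, event-free person-time. Time at risk averages 37.5 weeks for completers and 10.1 weeks for leavers. At 30% v 20% dropout:

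- More-dropout arm: 0.287 / (0.30 × 10.1 + 0.70 × 37.5) = 0.287 / 29.3 = 0.00979 per week.
- Other arm: 0.291 / (0.20 × 10.1 + 0.80 × 37.5) = 0.291 / 32.0 = 0.00909 per week.

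The ratio is 1.08 with no true difference. At 35% v 15% it is 1.16, and at 40% v 10% it is 1.25.

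**The case against.** The strongest objections, and what stands of each:

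- **Imbalance would be visible.** Withdrawals with reasons and exposure, the latter also in eight duration bands, are tabulated by arm. This stands, but a reader could not correct the event comparisons from those tables.
- **SAE follow-up does not stop at withdrawal.** A reader might infer that all safety observation ends at the ET Visit. It does not: SAEs run to 30 days after the last dose. An early leaver's SAE window is still much shorter than a completer's.
- **Patients who leave because of an AE are already counted**, both under that event and under TEAEs leading to discontinuation. This stands. Only events that would have come later are lost, and the model's independence of dropout and AEs is a simplification.
- **Many events come early.** The interim safety review, covering up to 16 weeks, already shows any TEAE in 80.4%, 65.2% and 78.75% of placebo, 300 mg and 600 mg patients. For early-onset events the distortion is slight, as the last column of the table shows.
- **The size depends on the assumed timing and splits.** This also stands, which is why a range is given. The 40% v 10% split is an extreme illustration, and a near-disappearance of a true excess (1.07) needs that split with every leaver gone by week 26.
- **This is a phase 2b trial with descriptive safety tables and no AE test.** That lowers the priority but does not remove the gap.

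**Conclusion.** The gap is real and conditional. Both documents summarise AEs without regard to time at risk, in a trial that assumes 25% dropout and stops non-serious AE collection at the ET Visit. If dropout differs by arm, later or ongoing risk is understated in the arm that loses more patients. Under the assumptions above, the null crude risk ratio lies between 0.95 and 0.77 for a constant hazard, and between 0.985 and 0.956 for events confined to the first 8 weeks. Equal dropout gives no bias between arms.

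A reader might go further and infer from the nausea figures that the 600 mg arm will look safer than it is. The documents do not support that. They give no dropout by arm, describe the nausea as mild, and report no notable difference in the overall safety profile at the interim. Nausea is also the kind of early event least affected, if its onset is early. Priority is low to moderate.

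**What to change.** In SAP 3.6.1 keep every planned percentage and count. For any TEAE, drug-related TEAEs, TESAEs, TEAEs leading to discontinuation, and preferred terms in at least 5% of an arm, add:

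- cumulative incidence of first event to Week 52, timed from first dose and censored at the end of AE collection;
- the difference from placebo with a 95% CI for each dose.

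Define the end of collection separately for AEs and SAEs, because their windows differ. Do not take the exposure variable in SAP 3.3.7 as time at risk: it runs to the last dose, ignores interruptions and leaves out post-dose observation.

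First-event rates per 100 patient-years may sit beside this, but should not be used alone for early-onset events such as nausea, where the constant-hazard assumption can create a false excess in the arm with more dropout.

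The cost is one SAP paragraph and one table from dates already collected, with no change to trial conduct. It should be specified before unblinding, so that the method is not chosen after dropout by arm is known. One limit remains: censoring still assumes that leavers would have had the same later risk as those who stayed, so the withdrawal-reason table should be read alongside.

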### **Interim Analysis**

An interim analysis was planned for this study after 90 patients had completed 16 weeks of treatment. This analysis was reviewed by the DSMC according to the DSMC Charter. The interim analysis included a comprehensive review of the following data: ALT, AST, HOMA-IR, Pro-C3, ELF panel, MRI-PDFF, cT1, and lipid parameters. The conclusions and recommendations of the DSMC were shared blindly with the Sponsor and clinical sites. A separate interim analysis plan was finalized prior to conducting the interim analysis.

### **Data Safety Monitoring Committee**

An external, independent DSMC will review all available unblinded preliminary safety and biomarker results, as described in the DSMC Charter. The DSMC Charter will describe the overall guidelines, composition and roles, and responsibilities of the independent DSMC for the NST-02 study, including the selection of DSMC members, timing of meetings, methods of providing information to and from the DSMC, frequency and format of meetings, data analysis recommendations, and DSMC relationships with other parties participating in the conduct of this study. Patient accrual will continue throughout the period of the DSMC review. The DSMC will advise on the accrual of the remaining patients per protocol or any amendments that are necessary for safety reasons.

### **SAMPLE SIZE DETERMINATION:**

A sample size of 88 patients per treatment group provides 80% power to detect a 40% responder rate for active versus placebo, assuming a placebo response rate of 18% and a dropout rate of 25%.

**SITES:** Approximately 50 sites in the United States

### LIST OF ABBREVIATIONS AND DEFINITION OF TERMS

Abbreviation	Definition
AA	Arachidonic acid
ACC	American College of Cardiology
AESI	Adverse events of special interest
AHA	American Heart Association
ALP	Alkaline phosphatase
ALT	Alanine aminotransferase
ASCVD	Atherosclerotic Cardiovascular Disease
AST	Aspartate aminotransferase
AUDIT	Alcohol Use Disorders Identification Test
AUDIT-C	Alcohol Use Disorders Identification Test-Concise
BMI	Body mass index
CAP	Controlled attenuation parameter
CFR	Code of Federal Regulations
COVID-19	Coronavirus Disease 2019
CRA	Clinical Research Associate
CSR	Clinical Study Report
cT1	Iron-corrected T1
CTCAE	Common Terminology Criteria for Adverse Events
CYP	Cytochrome P450
DAG	Diglyceride
DSMC	Data Safety Monitoring Committee
ECG	Electrocardiogram
eCRF	Electronic case report form
EDC	Electronic Data Capture
eGFR	Estimated glomerular filtration rate
EIU	Exposure In Utero
ELF	Enhanced liver fibrosis
EPA	Eicosapentaenoic acid
ET	Early Termination
FPG	Fasting plasma glucose
FSH	Follicle-stimulating hormone
GCP	Good Clinical Practice
GGT	Gamma glutamyl transferase
GLP-1	Glucagon-like peptide-1
HbA1c	Hemoglobin A1c
hCG	Human chorionic gonadotropin
HCV	Hepatitis C virus

Abbreviation Definition

HETE Hydroxyeicosatetraenoic acid
HIV Human immunodeficiency virus

HOMA-IR Homeostatic Model Assessment for Insulin Resistance

hsCRP High-sensitivity C-reactive protein

ICF Informed consent form

ICH International Council for Harmonisation

IRB Institutional Review Board

IRT Interactive Response Technology

ITT Intent-to-Treat

LDL-C Low-density lipoprotein-cholesterol

LS Least square

mITT Modified Intent-to-Treat
MRI Magnetic resonance imaging

n-3 FA Omega-3 fatty acid

NAS Nonalcoholic Fatty Liver Disease Activity Score

NASH Nonalcoholic steatohepatitis PCR Polymerase chain reaction

PCSK9 Proprotein convertase subtilisin kexin 9

PD Pharmacodynamic

PDFF Proton density-fat fraction

PK Pharmacokinetic(s)

PP Per-Protocol

PPARα Peroxisome proliferator-activated receptor alpha

Pro-C3 N-terminal type 3 collagen propeptide

SAE Serious adverse event

SEDDS Self-Emulsifying Drug Delivery System

SGLT2 Sodium-glucose cotransporter-2

SUSAR Suspected Unexpected Serious Adverse Reaction

T2DM Type 2 diabetes mellitus

TEAE Treatment-emergent adverse event

TNF-α Tumor necrosis factor alpha

ULN Upper limit of normal

VCTE Vibration-controlled transient elastography

WHO World Health Organization

